##### 5.2.3.2 Partial response (PR)

Either criterion may be met.

- Decrease in Derkay anatomic score of 30 percent or greater
- Partial tumor response by imaging using RECIST 1.1 criteria

### 5.2.3.3 Progressive disease (PD)

Any criterion may be met.

- Increase in objective Derkay anatomic score of 50 percent or greater
- Disease progression by imaging using RECIST 1.1 criteria
- New or worsening symptoms attributable to growth of papillomas or new papillomas.

### 5.2.3.4 Stable disease

- Not meeting criteria for CR, PR, or PD.

### 5.2.4 Evaluation of Best Overall Response

The best overall response is the best response recorded from the start of the treatment until disease progression/recurrence (taking as reference for progressive disease the smallest measurements recorded since the treatment started). The patient's best response assignment will depend on the achievement of both measurement and confirmation criteria.

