Adverse Events c				X c	X c	X		X c	X	X d
Concomitant Medications c		X c	X c	X c	X c	X		X c	X	
Leukapheresis			X h	X i						
Avelumab			X	X	X			X		X

a End of Treatment studies will be performed 42 days (+/- 10 days) after the final Avelumab treatment.

b Complete H&P at baseline, directed H&P if clinically indicated before each dose (may include clinic-based flexible nasopharyngolaryngoscopy and/or tracheoscopy), directed H&P at response assessment.

c These procedures must be performed within 3 days before each dose of avelumab while on treatment.

- d Adverse events will be followed until return to baseline or stabilization of event.
- e If the screening and baseline tests were performed prior to 3 days before the first dose of avelumab they will need to be repeated before the start of treatment. Refer to section **2.2** for screening evaluation timing requirements.
- f Within 14 days prior to subject enrollment
- g Within 28 days prior to subject enrollment
- h Within 7 days prior to first dose of avelumab
- i 9-17 days after first dose of avelumab and before second dose of avelumab
- j 9-17 days after second dose of avelumab and before third dose of avelumab
- k 9-17 days after third dose of avelumab and before the Course 2 Cycle 1 Day 1 dose, if applicable
- l 9-17 days after last dose of avelumab
- m +/- 10 days
- n If imaging is used for response assessment
- o Tests performed for End of Course 1 time point that were completed within 7 days prior to the Course 2 Cycle 1 Day1 dose of avelumab do not need to be repeated for Course 2 Cycle 1 Day 1.
- p within 90 days prior to subject enrollment

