#### 5.2.3 Definition of disease response

##### 5.2.3.1 Complete Remission (CR)

All criteria must be met.

- No evidence of papillomas on physical exam and/or clinic-based flexible nasopharyngolaryngoscopy and/or tracheoscopy.
- No evidence of papillomas by exam under anesthesia (sedation or general anesthesia) with endoscopy and biopsies.
- Absence of disease by imaging if lesions are assessed by imaging.

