#### **For Patients with Measurable Disease (i.e., Target Disease)**

Target Lesions	Non-Target Lesions	New Lesions	Overall Response	Best Overall Response when Confirmation is Required*
CR	CR	No	CR	≥4 wks. Confirmation**
CR	Non-CR/Non-PD	No	PR	≥4 wks. Confirmation**
CR	Not evaluated	No	PR	
PR	Non-CR/Non-PD/not evaluated	No	PR	
SD	Non-CR/Non-PD/not evaluated	No	SD	Documented at least once ≥4 wks. from baseline**
PD	Any	Yes or No	PD	no prior SD, PR or CR
Any	PD***	Yes or No	PD	
Any	Any	Yes	PD	
* See RECIST 1.1 manuscript for further details on what is evidence of a new lesion.				
** Only for non-randomized trials with response as primary endpoint.				

\*\*\* In exceptional circumstances, unequivocal progression in non-target lesions may be accepted as disease progression.

Note: Patients with a global deterioration of health status requiring discontinuation of treatment without objective evidence of disease progression at that time should be reported as “*symptomatic deterioration.*” Every effort should be made to document the objective progression even after discontinuation of treatment.

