## **9 STATISTICAL CONSIDERATIONS**

The trial will be conducted using a Simon optimal two-stage design; the objective is to rule out a 5% complete response rate ( $p_0=0.05$ ) and target a 20% complete response rate ( $p_1=0.20$ ).

The design will use  $\alpha=0.10$  (10% chance of accepting a poor agent) and  $\beta=.10$  (corresponding to 90% power--and 10% chance of incorrectly rejecting a promising agent).

The first stage of accrual will consist of 12 evaluable patients. If 0/12 has a complete clinical response, then no further patients would be enrolled to that cohort. Should 1 or more patients in the first 12 have a complete response, then accrual would continue until a total of 37 evaluable patients have enrolled. If there are 1 to 3 complete responses in 37 patients, this would be considered unacceptably low, while if 4 or more patients have complete responses in 37 patients, then the results will be considered sufficiently promising for further evaluation. Under the null hypothesis (5% complete response rate), the probability of early termination is 54.0%.

It is anticipated that up to 2 patients per month may enroll onto this trial; thus, up to 2 years may be required to complete accrual. The trial would require up to 37 total evaluable patients; the accrual ceiling will be set at 40 patients to allow for a small number of inevaluable patients.

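### Complete response needs confirmation at 4 weeks or more, but the plan names no examination to provide it and section 9 does not say whether a counted response must be confirmed

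*Combined protocol and SAP*

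**What the plan says.** Section 5.2.4 ties best response to two conditions: "The patient's best response assignment will depend on the achievement of both measurement and confirmation criteria". Its table for patients with measurable disease gives a confirmation interval of at least 4 weeks for CR. A footnote limits this: "Only for non-randomized trials with response as primary endpoint". The trial is single-arm with CR as its primary endpoint, so it falls within that limit. Section 5.2.2 counts papillomas scored on the Derkay system as measurable, so the heading of the table is not confined to imaging patients.

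Section 5.2.3.1 defines CR by several criteria that must hold together. One is "No evidence of papillomas by exam under anesthesia (sedation or general anesthesia) with endoscopy and biopsies".

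On timing, sections 3.3.5 and 3.5 place EUAs before the first dose, at weeks 2 and 6 for everyone, and at week 12 for partial responders who continue. A patient in CR at week 6 stops treatment (section 3.1.1). Responder follow-up in section 3.3.6 lists clinic endoscopy, and imaging where used, but no EUA. Calendar footnote l puts the closing EUA 9 to 17 days after the last dose. Footnote a says: "End of Treatment studies will be performed 42 days (+/- 10 days) after the final Avelumab treatment".

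Section 9 sets the stage 1 rule: "Should 1 or more patients in the first 12 have a complete response, then accrual would continue". At the end, 4 or more CRs in 37 are called promising. It does not say whether these CRs must be confirmed.

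**The concern.** The confirmation rule, the CR definition, the examination schedule and the section 9 endpoint do not fit together. If confirmation means meeting the whole CR definition again, a patient whose CR first appears at either formal response assessment has no EUA that clearly falls late enough to provide it. If confirmation is set aside, a CR that returns within weeks counts in full, contrary to section 5.2.4.

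Both decision rules turn on very small counts. One reclassified patient can decide whether the trial goes past stage 1, or whether 3 CRs become 4 at the end. If the reading is settled after results are known, the stated error rates no longer describe the test.

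**Working it through.** **1. The plan's own figures.** Inputs from section 9: "the objective is to rule out a 5% complete response rate", "target a 20% complete response rate", and alpha described as "10% chance of accepting a poor agent"; stop at 0 of 12; promising at 4 or more of 37.

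- Early stop: (1 − p)^12. At p = 0.05 this is 0.95^12 = 54.0%, as stated.
- Probability of a promising result: the sum over x = 1 to 12 of P(X = x) × P(Y ≥ max(0, 4 − x)), with X binomial (12, p) and Y binomial (25, p). This gives 0.0935 at p = 0.05 (limit 0.10) and 90.2% at p = 0.20 (stated 90%).
- Expected sample size under the null: 12 + (1 − 0.540) × 25 = 23.5. A grid search returns this same design as optimal.

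The design figures are sound.

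**2. Is there an EUA at least 28 days after the one that first shows CR?**

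- CR first shown at week 6: footnotes k (end of Course 1) and l (end of treatment) give the same window, days 9 to 17 after dose 3. Two EUAs in that window are at most 17 − 9 = 8 days apart.
- CR first shown at week 12: no later EUA is listed.
- Papillomas already absent at week 2: with dose 3 on day 28, the week 6 EUA falls on days 37 to 45. The gap is 37 − 17 = 20 to 45 − 9 = 36 days, nominally 28.

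**3. Can the later clinic endoscopy confirm instead?** Days are counted from the last dose, with the EUA timed by footnote l.

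- First later visit, days 32 to 52: 32 − 17 = 15 to 52 − 9 = 43 days after the EUA; nominally 42 − 14 = 28.
- For an EUA on day e, the visit days that fall short of 28 number e − 4. Summed over e = 9 to 17 this is 5 + 6 + … + 13 = 81, out of 9 × 21 = 189 day pairs.
- Next 6-weekly visit, taken as day 84 ± 10: 74 − 17 = 57 to 94 − 9 = 85 days after the EUA; nominally 70. This always exceeds 28.
- Section 3.1.1 allows a two-week delay of a protocol biopsy. An EUA on day 17 + 14 = 31 reaches 28 days only on day 59, after day 52. The following visit is then 74 − 31 = 43 to 94 − 31 = 63 days later.

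A short first gap therefore delays confirmation by one visit. It does not lose the CR.

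**4. What the choice of reading could do.** Assume a true CR rate of 20%, with each CR confirmed with probability c. The documents give no value for c, so a range is shown, using the formulas in step 1 at p = 0.20 × c.

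| c | Confirmed CR rate | Stage 1 stop | Power |
|---|---|---|---|
| 1.0 | 20% | 6.9% | 90.2% |
| 0.9 | 18% | 9.2% | 85.7% |
| 0.75 | 15% | 14.2% | 75.1% |
| 0.5 | 10% | 28.2% | 44.7% |
| 0.25 | 5% | 54.0% | 9.3% |
| 0 | 0% | 100% | 0% |

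The effect also runs the other way. If 5% is the null rate of confirmed CR and c = 0.5, CRs at a single look occur at 0.05 / 0.5 = 10%. Counting them all passes the drug with probability 44.7% instead of 9.3%.

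**The case against.** The strongest reply is that no passage says confirmation must repeat the EUA. The section 5.2.4 table gives an interval, not an examination, and clinic endoscopy every 6 weeks can show that papillomas remain absent. The primary endpoint is also not explicitly tied to confirmed best response: section 9 does not cite section 5.2.4, and sections 3.1.1, 3.3.5 and 11.4.2 describe the closing EUA and biopsies as what validates a CR. The table is in RECIST terms, which section 5.2 assigns to imaging, so its application to Derkay-scored patients can be argued either way.

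These points stand, and they rule out a stronger reading. A reader might infer that no patient can ever be assigned CR, so that stage 1 must read 0 of 12 and power is zero. The documents do not support that. It requires confirmation by a repeat EUA and a section 9 count limited to confirmed CRs, and neither is stated. Even then there are exceptions: a CR present at week 2 could be confirmed at week 6, although section 3.1.1 places the first response assessment at week 6; endoscopy may be omitted where disease is inaccessible, with imaging in follow-up; and if footnote a governed the final EUA, that EUA would fall 15 to 43 days after the end-of-Course-1 one. Nor is it right that only one EUA is scheduled.

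The 81 of 189 day pairs (43%) should likewise not be read as a share of CRs lost. Equal weighting of days has no basis in the documents, and the next visit is always late enough.

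What the reply does not supply is the missing statement. Section 5.2.4 demands confirmation, nothing names the examination, and section 9 is silent.

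**Conclusion.** The primary endpoint is not fully defined. Under the strict reading, a CR first shown at week 6 or week 12 cannot be confirmed from the schedule. Under the loose reading, unconfirmed CRs count. The two can give different decisions at 1 of 12 and 4 of 37. If the true CR rate is 20% and 75% to 90% of CRs are confirmed, power is 75.1% to 85.7% and the stage 1 stop probability 14.2% to 9.2%, against 90.2% and 6.9% when all are. These are illustrations, since the confirmed fraction is unknown.

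The interval calculations assume footnote l for the closing EUA and follow-up visits counted from the last dose. The sample size and cut-offs are not in error. What needs settling, before the stage 1 decision, is which patients count.

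**What to change.** In sections 5.2.3.1, 5.2.4 and 9:

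- Define the primary-endpoint CR as all section 5.2.3.1 criteria met once, including the closing EUA, and confirmed by absence of papillomas on the first already scheduled clinic endoscopy (and/or imaging where that is the response assessment) at least 28 days after that EUA. State that no second EUA is needed. The confirming visit is the End of Treatment or first follow-up visit if it is late enough, otherwise the next 6-weekly one.
- State that a CR without a confirming examination, such as one followed only by telephone under footnote q, is not a confirmed CR. Report unconfirmed CRs in a sensitivity analysis.
- Apply this definition to both the 0 of 12 decision and the 4 of 37 test, and state that the 5% and 20% rates refer to it.
- Reconcile calendar footnotes a and l on the timing of the End of Treatment EUA.

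The cost is wording, with no added visit or procedure. The stage 1 decision may wait about 4 weeks (28 days) to 10 weeks (nominally 70 days, 85 at the edge of the windows) after the last closing EUA. Section 3.7.2 already provides a pause for review at that point. A CR that relapses before confirmation will not count. The Simon design figures need no change.

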#### **For Patients with Measurable Disease (i.e., Target Disease)**

Target Lesions	Non-Target Lesions	New Lesions	Overall Response	Best Overall Response when Confirmation is Required*
CR	CR	No	CR	≥4 wks. Confirmation**
CR	Non-CR/Non-PD	No	PR	≥4 wks. Confirmation**
CR	Not evaluated	No	PR	
PR	Non-CR/Non-PD/not evaluated	No	PR	
SD	Non-CR/Non-PD/not evaluated	No	SD	Documented at least once ≥4 wks. from baseline**
PD	Any	Yes or No	PD	no prior SD, PR or CR
Any	PD***	Yes or No	PD	
Any	Any	Yes	PD	
* See RECIST 1.1 manuscript for further details on what is evidence of a new lesion.				
** Only for non-randomized trials with response as primary endpoint.				

\*\*\* In exceptional circumstances, unequivocal progression in non-target lesions may be accepted as disease progression.

Note: Patients with a global deterioration of health status requiring discontinuation of treatment without objective evidence of disease progression at that time should be reported as “*symptomatic deterioration.*” Every effort should be made to document the objective progression even after discontinuation of treatment.

### **5.3 TOXICITY CRITERIA**

The following adverse event management guidelines are intended to ensure the safety of each patient while on the study. The descriptions and grading scales found in the revised NCI Common Terminology Criteria for Adverse Events (CTCAE) version 4.0 will be utilized for AE reporting. All appropriate treatment areas should have access to a copy of the CTCAE version 4.0. A copy of the CTCAE version 4.0 can be downloaded from the CTEP web site ([http://ctep.cancer.gov/protocolDevelopment/electronic\\_applications/ctc.htm#ctc\\_40](http://ctep.cancer.gov/protocolDevelopment/electronic_applications/ctc.htm#ctc_40)).

## **6 NIH REPORTING REQUIREMENTS/DATA AND SAFETY MONITORING PLAN**

### **6.1 DEFINITIONS**

Please refer to definitions provided in Policy 801: Reporting Research Events found [here](#).

### **6.2 OHSRP OFFICE OF COMPLIANCE AND TRAINING / IRB REPORTING**

#### **6.2.1 Expedited Reporting**

Please refer to the reporting requirements in Policy 801: Reporting Research Events and Policy 802 Non-Compliance Human Subjects Research found [here](#). Note: Only IND Safety Reports that meet the definition of an unanticipated problem will need to be reported per these policies.

#### **6.2.2 IRB Requirements for PI Reporting at Continuing Review**

Please refer to the reporting requirements in Policy 801: Reporting Research Events found [here](#).

### **6.3 NCI CLINICAL DIRECTOR REPORTING**

Problems expeditiously reported to the OHSRP in iRIS will also be reported to the NCI Clinical Director. A separate submission is not necessary as reports in iRIS will be available to the Clinical Director.

In addition to those reports, all deaths that occur within 30 days after receiving a research intervention should be reported via email to the Clinical Director unless they are due to progressive disease.

To report these deaths, please send an email describing the circumstances of the death to [name] at [[contact]](mailto:[contact]) within one business day of learning of the death.

### **6.4 NIH REQUIRED DATA AND SAFETY MONITORING PLAN**

#### **6.4.1 Principal Investigator/Research Team**

The clinical research team will meet every two weeks when patients are being actively treated on the trial to discuss each patient. Decisions about dose level enrollment and dose escalation if applicable will be made based on the toxicity data from prior patients.

All data will be collected in a timely manner and reviewed by the principal investigator. Events meeting requirements for expedited reporting as described in section 6.2.1 will be submitted within the appropriate timelines.

The principal investigator will review adverse event and response data on each patient to ensure safety and data accuracy. The principal investigator will personally conduct or supervise the investigation and provide appropriate delegation of responsibilities to other members of the research staff.

## **7 SPONSOR PROTOCOL/SAFETY REPORTING**

### **7.1 DEFINITIONS**

#### **7.1.1 Adverse Event**

Any untoward medical occurrence in a patient or clinical investigation subject administered a pharmaceutical product and which does not necessarily have a causal relationship with this treatment. An adverse event (AE) can therefore be any unfavorable and unintended sign (including an abnormal laboratory finding), symptom, or disease temporally associated with the use of a medicinal (investigational) product, whether or not related to the medicinal (investigational) product (ICH E6 (R2))

#### **7.1.2 Serious Adverse Event (SAE)**

An adverse event or suspected adverse reaction is considered serious if in the view of the investigator or the sponsor, it results in any of the following:

- Death,
- A life-threatening adverse event (see section 7.1.3)
- Inpatient hospitalization or prolongation of existing hospitalization
  - A hospitalization/admission that is pre-planned (i.e., elective or scheduled surgery arranged prior to the start of the study), a planned hospitalization for pre-existing condition, or a procedure required by the protocol, without a serious deterioration in health, is not considered a serious adverse event.
  - A hospitalization/admission that is solely driven by non-medical reasons (e.g., hospitalization for patient or subject convenience) is not considered a serious adverse event.
  - Emergency room visits or stays in observation units that do not result in admission to the hospital would not be considered a serious adverse event. The reason for seeking medical care should be evaluated for meeting one of the other serious criteria.
- Persistent or significant incapacity or substantial disruption of the ability to conduct normal life functions
- A congenital anomaly/birth defect
- Important medical events that may not result in death, be life-threatening, or require hospitalization may be considered a serious adverse drug experience when, based upon

appropriate medical judgment, they may jeopardize the patient or subject and may require medical or surgical intervention to prevent one of the outcomes listed in this definition.

### 7.1.3 Life-threatening

An adverse event or suspected adverse reaction is considered "life-threatening" if, in the view of either the investigator or sponsor, its occurrence places the patient or subject at immediate risk of death. It does not include an adverse event or suspected adverse reaction that, had it occurred in a more severe form, might have caused death. (21CFR312.32)

### 7.1.4 Severity

The severity of each Adverse Event will be assessed utilizing the CTCAE version 4.0.

### 7.1.5 Relationship to Study Product

All AEs will have their relationship to study product assessed using the terms: related or not related.

- Related – There is a reasonable possibility that the study product caused the adverse event. Reasonable possibility means that there is evidence to suggest a causal relationship between the study product and the adverse event.
- Not Related – There is not a reasonable possibility that the administration of the study product caused the event.

### 7.1.6 Adverse Events of Special Interest (AESI)

Myocarditis or other serious autoimmune AEs (even if such events are expected) that occur will be reported by the PI and/or study coordinator. These AEs will be submitted to the FDA Division of Antiviral Products (DAVP) by the sponsor.

## 7.2 ASSESSMENT OF SAFETY EVENTS

AE information collected will include event description, date of onset, assessment of severity and relationship to study product and alternate etiology (if not related to study product), date of resolution of the event, seriousness and outcome. The assessment of severity and relationship to the study product will be done only by those with the training and authority to make a diagnosis and listed on the Form FDA 1572 as the site principal investigator or sub-investigator. AEs occurring during the collection and reporting period will be documented appropriately regardless of relationship. AEs will be followed through resolution.

SAEs will be:

- Assessed for severity and relationship to study product and alternate etiology (if not related to study product) by a licensed study physician listed on the Form FDA 1572 as the site principal investigator or sub-investigator.
- Recorded on the appropriate SAE report form, the medical record and captured in the clinical database.

- Followed through resolution by a licensed study physician listed on the Form FDA 1572 as the site principal investigator or sub-investigator.

For timeframe of recording adverse events, please refer to section **6.1**. All serious adverse events recorded from the time of first investigational product administration must be reported to the sponsor.

### **7.3 REPORTING OF SERIOUS ADVERSE EVENTS**

Any AE that meets protocol-defined serious criteria or meets the definition of Adverse Event of Special Interest that require expedited reporting must be submitted immediately (within 24 hours of awareness) to OSRO Safety using the CCR SAE report form.

All SAE reporting must include the elements described in section **7.2**.

SAE reports will be submitted to the Center for Cancer Research (CCR) at: [[contact]](mailto:[contact]) and to the CCR PI and study coordinator. CCR SAE report form and instructions can be found at:

<https://ccrod.cancer.gov/confluence/pages/viewpage.action?pageId=157942842>

Following the assessment of the SAE by OSRO, other supporting documentation of the event may be requested by the OSRO Safety and should be provided as soon as possible.

